5.5.1 Data Collection and Follow-up for Withdrawn Subjects

All withdrawn and excluded participants are sent instructions to turn off location tracking & delete the RealLife Exp app. They are also informed that they can contact us to schedule an optional offboarding call if they would like assistance with this process. This optional offboarding call will be compensated for their time at a rate of \$15/hour. These participants will also be sent a link to submit geolocation data for a final time for an additional \$5 payment (estimated 20 minutes at a rate of \$15/hour).

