5.7 Safety Evaluation

We evaluated safety according to our original plan:

1. After collection of 60 participants (approximately 20 in each group) and 120 participants (approximately 40 in each group), we will use EMA data to identify:
 - a. The distribution (histogram) of each participant's daily cigarette consumption (cig/day) during the baseline period ($b0$)
 - i. Including each ppt's mean baseline consumption ($cigs/day_{b0}$) & standard deviation (SD_{b0})
 - b. The distribution (histogram) of each participant's daily cigarette consumption (cig/day) during weeks 3 and 4 of the intervention period ($i3-4$)
 - i. Including each ppt's mean consumption ($cigs/day_{i3-4}$) & standard deviation (SD_{i3-4}) for intervention weeks 3 and 4
2. Participants will be identified as "increased smokers" if their average daily cigarette consumption during the final 2 weeks of the intervention period is more than 3 standard deviations above their baseline mean
 - a. Increased smokers: $cigs/day_{i3-4} > (cigs/day_{i3-4} + 3SD)$
3. If the number of "increased smokers" in the Tobacco retailer condition is significantly ($p \leq .01$) greater than the number of "increased smokers" in the control condition, this will trigger the study team to reconvene for a reassessment with members of the study team, the Primary Investigator, the Co-Investigators who have expertise in tobacco research, and the external stakeholders. This may result in the termination of this arm of the study and reassignment of future participants to the other two groups. Additionally, as part of this review, we will reach out to the participants in all conditions who met the criteria for an "increased smoker" to offer additional counseling on smoking cessation resources. The group will further make a plan to mitigate future risks to participants.

6 Statistical Plan

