6.1 Sample Size and Power Determination

Our initial target was to obtain 60 complete datasets (meaning that participants finished Online Session 3, two fMRI sessions [before and after the intervention period], and also completed all 20 store visits) per intervention condition (total $N = 180$). Due to pandemic-related resource constraints and time delays, we were unable to reach this goal. We collected the maximum number of participants possible with the resources available from our grant. Prior to looking at the data, we elected to randomize more individuals into the experimental conditions than to the control condition, since less than 50% of participants typically completed all 20 store visits and provided fully complete datasets. Before we conducted any hypothesis testing, we reassessed power in consultation with our study team's biostatistician to determine which original hypotheses would be adequately powered with the available data and planned analysis.

methods. Using PANGEA, we estimated that with at least 40 complete datasets (participants who completed all 20 store visits) in each intervention condition, we could detect interaction effects (time * group) sized $d = 0.1$ with 95% power. We ultimately randomized 105 to the Non-tobacco retailer condition, 107 participants to the Tobacco retailer condition, and 70 participants to the Control condition resulting in 175 complete datasets. We scanned as many participants as we were able to obtain within constraints of the larger study. Power analysis suggests that with $N=32$ and at least 10 observations per condition in the fMRI dataset, per participant, we have $>80\%$ power to detect effects of $d = .2$ (i.e., a small effect size) within person.

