6.3.3 Interim Analysis

At two time points during data collection, we will assess whether the study is producing unexpectedly positive or negative effects on participant outcomes. After collection of 60 participants (approximately 20 in each group) and 120 participants (approximately 40 in each group), we will test whether individuals in the Tobacco retailer condition have significantly changed the number of cigarettes that they smoke per day (as described in 5.7). If this group of participants changes their cigarette consumption by a clinically significant level, we will stop assigning participants to that group and assign all further participants equally to the other groups.

7 Safety and Adverse Events

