7.1.2 Serious Adverse Event

Serious Adverse Event

Adverse events are classified as serious or non-serious. A serious adverse event is any AE that is:

- fatal
- life-threatening
- requires or prolongs hospital stay
- results in persistent or significant disability or incapacity
- required intervention to prevent permanent impairment or damage
- a congenital anomaly or birth defect
- an important medical event

7.2 *Recording of Adverse Events*

Smoking behavior will be self-reported at each study session and multiple times daily during the baseline and intervention periods. This data will be used at set points as described in section 5.7. Experimenters will record medical or other life events that may be considered adverse events as reported by participants (e.g., hospitalization or injury in between study sessions). Information on all adverse events will be recorded in the source document immediately upon discovery, and also in the appropriate adverse event module of the case report form (CRF). All clearly related signs, symptoms, and abnormal incidental findings results will be recorded in the source document.

All adverse events occurring during the study period will be recorded. The clinical course of each event will be followed until resolution, stabilization, or until it has been determined that the study intervention or participation is not the cause. Serious and related adverse events that are still ongoing at the end of the study period will be followed up to determine the final outcome. Any serious adverse event that occurs during an in-person session and is considered to be possibly related to the study intervention or study participation will be recorded and reported.

7.3 *Relationship of AE to Study*

- **Definitely Related** – There is clear evidence to suggest a causal relationship, and other possible contributing factors can be ruled out. The clinical event, including an abnormal laboratory test result, occurs in a plausible time relationship to study procedures administration and cannot be explained by concurrent disease or other drugs or chemicals. The response to withdrawal of the study procedures should be clinically plausible. The event must be pharmacologically or phenomenologically definitive.

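### Section 5.7 flags individuals as increased smokers, but the only response tied to the flag depends on an arm-level test, and later participants and early leavers are not classified

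*Combined protocol and SAP*

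**What the plan says.** **The flag.** Section 5.7 classifies a participant as an increased smoker if "their average daily cigarette consumption during the final 2 weeks of the intervention period is more than 3 standard deviations above their baseline mean". The formula printed beneath that sentence reads "Increased smokers: $cigs/day_{i3-4} > (cigs/day_{i3-4} + 3SD".

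**The looks.** They come "After collection of 60 participants (approximately 20 in each group) and 120 participants (approximately 40 in each group". Section 6.3.3 repeats the number: "At two time points during data collection, we will assess whether the study is producing unexpectedly positive or negative effects on participant outcomes". Neither section plans a later look.

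**The trigger.** Under 5.7 the team reconvenes if flags in the Tobacco retailer arm significantly exceed those in Control at p ≤ .01. That review may end the arm, and contact is one of its parts: "as part of this review, we will reach out to the participants in all conditions who met the criteria for an" increased smoker. Section 6.3.3 describes the consequence differently: a clinically significant change in the Tobacco arm means that assignment to it stops.

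**Use of smoking data for safety.** Section 7.2 says of self-reported smoking: "This data will be used at set points as described in section 5.7". Section 7.4.3 says adverse events are monitored in real time.

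**Leavers.** Sections 5.5.1 and 5.6 provide instructions on switching off tracking and removing the app, and an optional paid call to help with this. They add: "These participants will also be sent a link to submit geolocation data for a final time for an additional" $5. No smoking question is mentioned.

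**General provision.** Section 5.3.3 gives participants at Session 3 a Quit Resources document. Those interested in the scan receive it after the scan, or once they are found ineligible for it.

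**Numbers.** Section 6.1: "We ultimately randomized 105 to the Non-tobacco retailer condition, 107 participants to the Tobacco retailer condition, and 70 participants to the Control condition", giving 175 complete datasets.

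**The concern.** Increased smoking is the harm that section 5.7 was written to catch, and EMA measures smoking several times a day in every participant. The flag is individual, because it compares a person with their own baseline. The response is collective, because it waits for a significant difference between two of the three arms. That comparison says little about whether a given person's smoking rose. Once the trigger fires, 5.7 provides for contacting flagged people in every arm, so the plan already treats a flag as relevant in all three.

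Two groups fall outside the scheme: participants who come after the last look, and those who leave before the weeks that the criterion needs. At stake is whether the trial can account for the individual increases that it measured, and whether its safety report covers everyone randomised.

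**Working it through.** **Inputs.** Looks at 60 and 120 with about 20 and 40 per group, and alpha .01 (5.7). Randomised 105, 107 and 70; 175 complete datasets (6.1). The plan gives no operating figure for the trigger, so there is none to reproduce. Its simple arithmetic agrees: 60/3 = 20, 120/3 = 40, and 105 + 107 + 70 = 282.

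**1. Flags that can pass without outreach.** Neither the test nor its sidedness is named, so four versions were tried. The table gives the smallest Tobacco count that reaches p ≤ .01 with no flag in Control.

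| Test | 20 v 20 | 40 v 40 |
|---|---|---|
| Fisher exact, two-sided | 7 | 8 |
| Fisher exact, one-sided | 7 | 7 |
| Uncorrected z, two-sided | 6 | 7 |
| Uncorrected z, one-sided | 5 | 6 |

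The largest count without outreach is one less: 4 to 6 of 20 at look 1, and 5 to 7 of 40 at look 2. The case of 6/20 v 0/20 shows the dependence on the test:
- Fisher one-sided: p = C(20,6)/C(40,6) = 38,760/3,838,380 = .0101, which just misses. Two-sided it is .0202.
- Uncorrected z: 0.30/√(0.15 × 0.85 × 2/20) = 2.66, two-sided p about .008, which fires.

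One Control flag at 40 v 40 raises the required count to 10 or 9 (Fisher, two- or one-sided) or 9 or 8 (z). Nontobacco flags enter none of these calculations.

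**2. Chance that the trigger fires at look 2.** The documents give no flag rates, so these are assumptions (Fisher, 40 v 40).

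| Tobacco v Control flag rate | Two-sided | One-sided |
|---|---|---|
| 10% v 1% | 2.9% | 7.1% |
| 20% v 5% | 17% | 27% |
| 20% v 1% | 45% | 60% |
| 30% v 5% | 57% | 70% |

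At 10% v 1%, with Nontobacco also at 1%, 40 × 0.10 + 80 × 0.01 = 4.8 people would be flagged among 120, and the trigger would seldom fire.

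**3. Participants after the last look.**
- If looks count complete datasets: 175 − 120 = 55, and 55/175 = 31%.
- If looks count randomised participants: 282 − 120 = 162, and 162/282 = 57%.

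The documents do not say which applies. If looks count people with weeks 3-4 EMA, the share lies between these figures, because 6.1 also requires all 20 store visits for a complete dataset.

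**4. Early leavers.** The flag needs a mean over weeks 3-4. Someone who leaves before week 3 has none and cannot be classified. Someone who leaves during weeks 3-4 might be, but no rule is given. The number in either group is not stated.

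**5. The printed formula.** It has the weeks 3-4 mean on both sides. Subtracting it leaves 0 > 3SD, which is never true. Read literally, nobody is flagged. Section 5.7 also defines two SDs, baseline and weeks 3-4, and the formula does not say which it uses.

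**The case against.** The strongest reply is that participants are not left without provision. Session 3 brings the Quit Resources document whatever a person's smoking, the investigator may stop participation for safety or health (5.5), and adverse events are monitored in real time (7.4.3). This stands against a reading that a reader might infer, that measured harm goes wholly unanswered. The documents support less than that: no response is tied to the flag outside a triggered review. The Quit Resources document does not depend on the flag, it can come after a scan held up to 6 months later (4.1), and leavers are not stated to receive it.

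Other tempting readings also go too far:
- **The trial outgrew its looks, 180 planned against 282.** These are different units. The target of 180 was complete datasets, and the like-for-like figure obtained is 175.
- **Leavers are the people most likely to have been harmed.** No passage links leaving to increased smoking.
- **The 282 − 175 = 107 without complete datasets are leavers.** A participant in a store arm can miss completeness by missing store visits.
- **Smoking is never examined after the 120th participant.** Later participants still give EMA data and enter the Hypothesis 2 model. Section 7.2 does not say that the set points are the only use. What these participants lack is classification by the flag.

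It is also fair to say that enrolment is complete (343 actual), so prospective flagging or a new question for leavers is no longer possible in this trial. Retrospective classification and clear reporting still are.

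**Conclusion.** The point holds as a gap in the plan. The only response linked to an individual flag depends on a Tobacco-versus-Control test that ignores the Nontobacco arm. With no Control flags, that test can leave as many as 4 to 6 of 20, or 5 to 7 of 40, flagged Tobacco participants without outreach. Between 31% and 57% fall after the last look, depending on what the looks count, and people who leave before week 3 cannot be classified at all.

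The threshold counts assume the equal groups of 20 and 40 stated in 5.7. Section 6.1 says that fewer people were randomised to Control, so actual group sizes at the looks may have differed. The firing probabilities rest on assumed flag rates.

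A reader might infer that people were harmed and then overlooked. The documents do not show this: 5.7 says that safety was evaluated to plan but does not report whether anyone was flagged or whether the trigger fired.

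**What to change.** 1. **Correct the printed criterion** in 5.7 so that it matches the sentence above it (own baseline mean plus 3 SD), and name the SD. Name the arm-level test and its sidedness, and say what the 60 and 120 count.
2. **Apply the criterion to the existing EMA data of all 282 randomised participants.** Report flagged and unclassifiable counts by arm. Add a sensitivity count that uses the last available intervention EMA for early leavers.
3. **Reconcile four sections:** 5.7 (outreach only within a triggered review, and the arm may be ended), 6.3.3 (assignment to the arm stops), 7.2 (smoking data used at set points) and 7.4.3 (real-time monitoring). The text should make clear whether an individual flag gets a response that does not depend on the arm-level p-value. Whether, when and how flagged people are contacted is for the study team, Study Physician and IRB.

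**Cost.** A small amount of analysis on data already held, plus wording. The flag uses only a person's own EMA, so computing it reveals no arm. In a future trial, contact when EMA closes could come before Session 3, which includes self-reported consumption and the cue reactivity task, and before the fMRI scan. It could affect those outcomes, so its timing would need thought.

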6.1 Sample Size and Power Determination

Our initial target was to obtain 60 complete datasets (meaning that participants finished Online Session 3, two fMRI sessions [before and after the intervention period], and also completed all 20 store visits) per intervention condition (total $N = 180$). Due to pandemic-related resource constraints and time delays, we were unable to reach this goal. We collected the maximum number of participants possible with the resources available from our grant. Prior to looking at the data, we elected to randomize more individuals into the experimental conditions than to the control condition, since less than 50% of participants typically completed all 20 store visits and provided fully complete datasets. Before we conducted any hypothesis testing, we reassessed power in consultation with our study team's biostatistician to determine which original hypotheses would be adequately powered with the available data and planned analysis.

methods. Using PANGEA, we estimated that with at least 40 complete datasets (participants who completed all 20 store visits) in each intervention condition, we could detect interaction effects (time * group) sized $d = 0.1$ with 95% power. We ultimately randomized 105 to the Non-tobacco retailer condition, 107 participants to the Tobacco retailer condition, and 70 participants to the Control condition resulting in 175 complete datasets. We scanned as many participants as we were able to obtain within constraints of the larger study. Power analysis suggests that with $N=32$ and at least 10 observations per condition in the fMRI dataset, per participant, we have $>80\%$ power to detect effects of $d = .2$ (i.e., a small effect size) within person.

6.2 Statistical Methods

Behavioral data (ecological momentary assessment, smoking behavior) as well as neural activity aggregates from regions of interest will be analyzed using the statistical software R. Data will be analyzed using multi-level regression and repeated measures ANOVA, or alternative appropriate statistics, given observed distributions.

fMRI data will be analyzed using Statistical Parametric Mapping (SPM; Wellcome Trust Centre for Neuroimaging) and NiPype. We will examine neural responses to tobacco marketing and to other smoking-related images, and how these responses relate to tobacco marketing exposure in the real-world, as well as group differences in these responses.

Prior to analysis, we will apply standard data screening/cleaning procedures to: (a) screen for data-entry errors, (b) check for outliers, (c) assess the extent and pattern of missing data, (d) create all summary scores needed for analysis, and (e) check that appropriate assumptions of normality are met. The assumptions underlying the application of all the statistical methods that are used will be examined, principally through the use of standardized residuals, influence diagnostics, and graphical displays. Neuroimaging analysis will be done in nipype and SPM12, beginning with slice-time correction, realignment, coregistration of functional and structural images, and normalization to the standard Montreal Neurological Institute (MNI) brain. This processing will include image quality assessment (QA) procedures that examine global and ROI based raw and processed temporal signal-to-noise ratio, absolute and relative motion, and visual inspection. Response amplitude (percent signal change) within each ROI will be extracted using SPM or nipype tools; primary tests of our aims will be performed in R, $\alpha=.05$, two tailed. Whole-brain exploratory analyses will be performed in SPM12, thresholded to correspond to $p<.05$, FDR-corrected.

6.3 Control of Bias and Confounding

Participants who complete the required tasks during the baseline period (Period 1) will be randomized. All participants must be able to complete tasks in any condition to participate, and so all participants have an equal chance to be in any of the conditions. Conditions are coded with a numeric value so they can be analyzed by researchers blinded to the participants' specific group assignment.

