4.1 Duration of Study Participation

The target behaviors (smoking frequency, cravings for cigarettes) will be assessed for an approximately 2 week baseline period and for an approximately 4 week intervention period. Thus, total study participation is expected to be approximately 6 weeks of active participation, with possible breaks in between the baseline and intervention periods. Total duration of

participation will thus be approximately 2 months, with some exceptions (such as pauses in active participation because of the University's special winter vacation, or as requested by participants due to external constraints). A subset of participants will be invited to complete an optional fMRI scan after their final online session; flexibility will be allowed in the timing of the scan session, which can be as long as 6 months after the final online session. This subset of participants will participate for a longer duration (total duration of participation can be up to 8 months [2 months of active participation, with a scan session up to 6 months later]).

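### Section 6.3 claims equal chances of every condition, but section 6.1 reports unequal allocation; if the ratio changed part-way, the Control contrasts need an allocation-period term that the models lack

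*Combined protocol and SAP*

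**What the plan says.** Section 6.3 (Control of Bias and Confounding) reasons from the requirement that everyone be able to do the tasks of any condition to the conclusion that "all participants have an equal chance to be in any of the conditions".

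Section 6.1 (Sample Size and Power Determination) says otherwise: "we elected to randomize more individuals into the experimental conditions than to the control condition". The reason given is "since less than 50% of participants typically completed all 20 store visits and provided fully complete datasets", and the choice is placed before any look at the data. The result: "We ultimately randomized 105 to the Non-tobacco retailer condition, 107 participants to the Tobacco retailer condition, and 70 participants to the Control condition".

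Other sections point to an equal starting plan. Section 6.1 opens with "Our initial target was to obtain 60 complete datasets" per condition, and the safety looks in sections 5.7 and 6.3.3 are set "After collection of 60 participants (approximately 20 in each group) and 120 participants (approximately 40 in each group"). Section 3.2 reports a different change during the trial, from fully random to blocked allocation on 12/01/2022, and mentions no ratio. No section dates the move away from Control or states the ratio used before or after it.

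In section 6.3.2, the Level-2 equations for Hypotheses 1 and 2 contain only the two condition dummies and random effects, for both the intercept and the StudyPhase slope. There is no calendar or allocation-period term.

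**The concern.** Two things follow. First, the equal-chance sentence cannot be right as written for Control, yet it stands in the section on control of bias.

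Second, if the probability of Control fell during recruitment, Controls were on average recruited earlier than store-arm participants. Assignment is still random within each period of constant ratio, but pooling the periods without a period term mixes a condition effect with an early-versus-late effect. Tobacco vs Control (gamma11) is one of the two key contrasts for both craving and smoking. Tobacco vs Nontobacco (gamma21) would be practically untouched, so a disagreement between the two contrasts could partly reflect timing.

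The mechanism is narrow. Both key terms are phase-by-condition interactions, so each person serves as their own control. A stable difference in smoking or craving level between early and late recruits is absorbed by the baseline terms and cancels. Only a difference between periods in the baseline-to-intervention change gets through. Season, stage of the pandemic or recruitment source could produce one; the documents neither show nor exclude it.

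**Working it through.** **Inputs.** Randomised: Tobacco 107, Nontobacco 105, Control 70, total 282 (section 6.1). Equal starting plan: 60 complete datasets per condition (6.1), about 20 and 40 per group at the looks (5.7, 6.3.3). Test: two-sided 5% (6.2). The switch point and the drift are not in the documents and are assumed over a range.

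**Step 1: is 105/107/70 compatible with equal chances throughout?** Expected count per arm = 282/3 = 94. Chi-square = (11² + 13² + 24²)/94 = 866/94 = 9.21 on 2 df, p = 0.010. Exact binomial: P(Control ≤ 70 of 282 at 1/3) = 0.0012. The split agrees with section 6.1 and not with 6.3. This does not show that the ratio changed over time; unequal allocation from the first participant would fit equally well.

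**Step 2: how far would the arms differ in timing?** Assume the first n1 participants were allocated exactly 1:1:1 and the rest under a new ratio. The share of an arm of size N randomised after the switch is (N − n1/3)/N. The Tobacco-minus-Control gap is therefore (n1/3) × (1/70 − 1/107).

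| n1 | Tobacco after switch | Control after switch | Gap |
|---|---|---|---|
| 0 | 100% | 100% | 0 |
| 60 | 87/107 = 81.3% | 50/70 = 71.4% | 9.9 points |
| 120 | 67/107 = 62.6% | 30/70 = 42.9% | 19.8 points |
| 180 | 47/107 = 43.9% | 10/70 = 14.3% | 29.6 points |
| 210 | 37/107 = 34.6% | 0/70 = 0% | 34.6 points |

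The last row is the limit, because 210/3 = 70 uses up all Controls. The Tobacco-minus-Nontobacco gap is at most 37/107 − 35/105 = 1.2 points.

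**Step 3: bias.** Bias in Tobacco minus Control (the negative of gamma11, since Tobacco is the reference) = gap × drift, where drift is the between-period difference in mean baseline-to-intervention change, in SD of change. At n1 = 120:

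- drift 0.2: 0.198 × 0.2 = 0.04 SD
- drift 0.4: 0.198 × 0.4 = 0.08 SD

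Nontobacco vs Control is affected almost equally (gap at n1 = 120: 65/105 − 30/70 = 19.0 points).

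**Step 4: type I error.** The standard error of the contrast is √(1/107 + 1/70) = 0.154 SD. Simulating the contrast in change at n1 = 120 (20,000 runs) gave 5.8% at drift 0.2 and 7.4% at drift 0.4. The normal formula P(|Z + bias/SE| > 1.96) gives 5.8% and 8.1%; it is a little higher at 0.4 because it ignores the extra variance that drift adds within arms. With the period term added (5,000 runs), the bias returned to about 0 and the error to about 5%.

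**Step 5: what it would take to be worse.** With n1 = 210 and drift 0.3, bias = 0.346 × 0.3 = 0.10 SD and the normal formula gives about 10%; with drift 0.5, bias is 0.17 SD and the error about 20%. Both need Control closed after 210 participants, which nothing in the documents states.

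**The case against.** **The change of ratio is inferred.** The rate of completing store visits need not have come from this trial's own participants. Section 4.2 already expected 400 enrolled to yield 180 evaluable (45%), section 5.1.1 mentions a related in-person study, and section 6.3.2 a pilot dataset. The 60 per condition are complete datasets rather than numbers randomised, and the 20 and 40 per group can be read as participants collected. If allocation was unequal from the start, the timing gap is zero. This stands: a change part-way is the most natural reading, but it is not established, and the honest range starts at 0.

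**The sentence in 6.3 may mean only that everyone was eligible for every arm.** That is a fair account of its intent. Eligibility does not give equal probability, though, and the sentence draws that conclusion. It needs rewording in any case.

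**The drift is assumed and may be small.** This also stands. The winter pauses in section 4.1 ("pauses in active participation because of the University's special winter vacation") are weak support, because nothing ties them to one allocation period and a before/after indicator would not adjust for season.

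**Stronger readings to avoid.** A reader might infer that Control was cut back in response to outcomes. Section 6.1 says "Prior to looking at the data, we elected to randomize more individuals", and nothing contradicts it. A reader might also infer that Tobacco vs Control is broadly a comparison of calendar periods, or has lost the protection of randomisation. The documents do not support that either: level differences cancel, and within any period of constant ratio the comparison remains randomised.

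**Conclusion.** The contradiction between 6.3 and 6.1 is certain and should be corrected. The bias is conditional. It needs a ratio that changed during recruitment, which the text strongly suggests but does not date, and a difference between periods in the baseline-to-intervention change, for which there are no data. Given both, it falls on Tobacco vs Control and, almost equally, on Nontobacco vs Control, for craving and smoking alike.

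Its size runs from nothing (ratio constant throughout) through a modest inflation of type I error (central case above) to something material only with a late switch and large drift. The calculation assumes a single switch from exactly 1:1:1. The missing date and ratio are known only to the study team, and without them a reader cannot judge gamma11.

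**What to change.** 1. Replace the equal-chance sentence in section 6.3 with the allocation ratio or ratios actually used and the dates of each, and say whether any change coincided with the start of blocking on 12/01/2022.
2. If the ratio changed, add an allocation-period indicator to the Level-2 equations for both the intercept and the StudyPhase slope in Hypotheses 1 and 2, so that conditions are compared within periods of constant allocation probability.
3. If Control was closed at any time, base the Control contrasts only on participants randomised while it was open.
4. If the ratio was unequal but constant, say so; step 1 then suffices.

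**Cost.** No new data: the period follows from the randomisation date. Each outcome model gains two terms, at one or two degrees of freedom. In a simple three-arm regression of change on arm and period, the standard error of Tobacco vs Control rises from 0.1537 to 0.1556 SD with a switch at 120 (about 1%) and to 0.1584 SD at 180 (about 3%). Restriction to concurrent participants costs more: in the extreme case of 70 per arm, √(2/70) = 0.169 against 0.154, about 10% wider.
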